Development of a M-Health Smokeless Tobacco Cessation Intervention for Firefighters

Document Date: 2/22/2024

NCT05111041

Purpose of the Study

The specific aims are:

Aim 1: In collaboration with the Professional Firefighters and Paramedics of North Carolina and our Advisory board of firefighters, develop a mHealth smokeless tobacco cessation intervention tailored to the specific needs of first responders such as firefighters and EMTs / paramedics. Using a co-facilitated user centered design approach and guided by the Spiral Technology Action Research Model (STAR) Model, we will work with firefighters & EMTS / paramedics to 1) identify and develop intervention content, messaging, and m-health modalities for delivery (e.g., text-messaging, text-chat); 2) refine the intervention; and 3) conduct usability testing. The outcome of Aim 1 will be a fully developed mHealth smokeless tobacco cessation intervention tailored to the unique needs of first responders (e.g., firefighters and EMTs) that is ready for pilot testing.

Aim 2: To assess the feasibility, acceptability, and preliminary efficacy of the tailored smokeless tobacco cessation intervention compared to a usual care control intervention in decreasing smokeless tobacco use. This aim will specifically address recruitment and retention to determine feasibility, acceptability as measured by the usefulness of the intervention received, and preliminary efficacy of the intervention in improving smokeless tobacco cessation at 30-days post intervention completion as measured by self-reported abstinence from smokeless tobacco use. This evaluation will be done with 50 firefighters & EMTs / paramedics who use smokeless tobacco who will be randomized to the tailored mHealth intervention (n=25) or the usual care control (n=25) of a self-help booklet. Both the intervention and control group will be given a 4 week supply of NRT lozenges with instructions of how to use.

Background & Significance

Firefighters are at high risk for cancer

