mHealth Intervention: Although the specific content, messaging and delivery strategy will be developed with firefighters and EMTs, the proposed mHealth intervention will incorporate evidenced-based strategies for cessation and theoretical constructs from the Social Cognitive Theory and the Health Belief Model that have been shown to support cessation. The intervention will contain key steps to quitting including: 1) supporting readiness and motivation to quit; 2) setting a quit date and constructing a quit plan; 3) dealing with withdrawal symptoms and triggers to use; and 4) maintaining quit status and avoiding relapse.

Participants will identify on the baseline survey whether they would prefer to quit by reduction or by abrupt cessation. All participants will receive support messages and NRT. All participants (including the control group) will receive an NRT lozenge guide (to provide instructions to all participants to create a consistent use for all). This will be included when the NRT lozenges are sent out to each study participant.

Abrupt Cessation: Participants are asked to set a quit date within two-four weeks. This quit date is emailed to participants. Participants will receive 8 weeks of messages. Pre-quit messages will focus on health benefits of quitting, building confidence, and making a quit plan. Post-quit messages will focus on dealing with cravings and urges and relapse prevention.

Reduction Cessation: Participants will receive a text at the beginning of each week alerting them to their number of dips for each day that week. They will receive a message reminder in the morning: "Do your best to only dip X times today, limit dip in your mouth to 30 minutes." At the end of each day participants will be asked to report how many times they dipped that day.

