Text-based Cessation Support Intervention: Participants will receive text-based support messages 2-3 times per day over ten weeks. The messages are based on constructs of Social Cognitive Theory the Health Belief Model and the Theory of Self-regulation. Messages were developed from our pilot work with firefighters and address salient features that are associated with smokeless tobacco use in this population such as stress. The text-based system with have interactive capabilities, participants can text the word CRAVE if they are having a craving and will receive a message to help them deal with the craving. Participants can also text the word SLIP if they have a slip after their quit date and will receive a message to get them back on track. Participants can text MOOD if they need a positive message to boost their mood. Finally, participants can text the word CALL, a feature that can be used to address the stress that is commonly felt post-call. Messages will focus around providing mindfulness and deep breathing activities to deescalate after participating in a call.

Nicotine Replacement Therapy: We will provide participants via mail nicotine replacement the nicotine lozenge at no cost. We will provide a 4 week supply of 4mg Lozenge (mirroring the dose and the length to similar studies with smokeless tobacco users) with instructions on how to use. Participants will be instructed via text to start their NRT on their quit date. Participants will be instructed to use the lozenges every day for 12 weeks. For the first 6 weeks, use 1 lozenge every 1-2 hours. For the next three weeks, use 1 lozenge every 2-4 hours. For the last three weeks, use 1 lozenge every 4-8 hours. They should not use more than 5 lozenges in 6 hours, or more than 20 lozenges total per day. For any side effects potentially related to use of the nicotine replacement, we will instruct participants to stop using the lozenge and contact the study phone number to speak to a registered nurse (PI is a registered nurse). We will explain side effects that include nausea, light-headedness, headache, poor sleep, mouth sores and heart palpitations. We will explain that severe side effects (vomiting, syncope, tachycardia) related to use of the nicotine replacement are rare; however, we will make participants aware of these and will instruct them to contact the PI (a registered nurse) if they occur.

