Motivational Text-Messages: To deliver the most equivalent intervention to the original Enough Snuff Program, we will send participants motivational text messages that map to the content of the phone counseling sessions. One week after the cessation booklet is sent we will text participants twice a week for the next 10 weeks. These are separate texts than what the intervention group will receive and coincide with the Enuf Snuff booklet. We will model the messages after the phone content and messages will focus on: motivation to quit, setting a quit date, picking a quit plan, motivation to follow-through with plan and dealing with tough situations when quitting. Messages will refer to the Enough Snuff booklet ask for a response from participants. We chose to send text messages to participants instead of phone calls as texting is consistent with our mode of contact with participants, less expensive, expands our reach, and is highly acceptable according to our pilot work.

Nicotine Replacement Therapy: We will provide participants via mail nicotine replacement the nicotine lozenge at no cost. We will provide a 4 week supply of 4mg Lozenge (mirroring the dose and the length to similar studies with smokeless tobacco users) with instructions on how to use. Participants will be instructed via text to start their NRT on their quit date. Participants will be instructed to use the lozenges every day for 12 weeks. For the first 6 weeks, use 1 lozenge every 1-2 hours. For the next three weeks, use 1 lozenge every 2-4 hours. For the last three weeks, use 1 lozenge every 4-8 hours. They should not use more than 5 lozenges in 6 hours, or more than 20 lozenges total per day. For any side effects potentially related to use of the nicotine replacement, we will instruct participants to stop using the lozenge and contact the study phone number to speak to a registered nurse (PI is a registered nurse). We will explain side effects that include nausea, light-headedness, headache, poor sleep, mouth sores and heart palpitations. We will explain that severe side effects (vomiting, syncope, tachycardia) related to use of the nicotine replacement are rare; however, we will make participants aware of these and will instruct them to contact the PI (a registered nurse) if they occur.

Measures

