Randomization: Eligible participants will be randomized to either the mHealth Intervention (N=25) or control (N=25) group. Computerized randomization will be used to deliver a permuted block randomization with block sizes of four that will be used to randomly assign participants to one of the two intervention groups. The randomization scheme generated by the study statistician will be administered using the REDCap system. We will also use a graded compensation for surveys with \$15 for baseline and \$20 for 30-days post end of program.

Risk/Benefit Assessment

This is a minimal risk study. The only risks are the potential for emotional distress in answering questions about smokeless tobacco use and the risk associated with smokeless tobacco use, and the potential loss of confidentiality. Every precaution will be taken to minimize these risks, including the ability to contact the PI for questions or concerns, and using encrypted devices to record PHI.

All participants may decline to be part of the study and may leave the study at any time without loss of benefit to which they are entitled.

The focus groups will be conducted in the firefighters' home station or individually via Zoom. Participants in focus groups will be familiar with each other and will be free to respond or not respond. Firefighters and EMTs will have the PI's email address and can message if they prefer to respond privately.

Intervention participants may choose the time and the place to take their surveys and respond or not respond to Mosio secure text messages. This will ensure their comfort with the privacy available to them. All study platforms will be secure and approved by Duke OIT, helping to ensure participant response confidentiality.

The potential benefits outweigh risks. Those who participate in the intervention have a high probability of benefitting if they decrease or cease using smokeless tobacco.

Data Analysis & Statistical Considerations

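### The closed list of risks leaves out the nicotine lozenges mailed to both arms, and nothing planned systematically records lozenge side effects or stopping

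*Combined protocol and SAP*

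**What the plan says.** The Risk/Benefit Assessment calls the study minimal risk and then gives a closed list: "The only risks are the potential for emotional distress in answering questions about smokeless tobacco use and the risk associated with smokeless tobacco use". Its one further entry is a breach of confidentiality. The lozenge is not mentioned.

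Elsewhere the lozenge is part of the treatment of every randomized participant. Aim 2 says: "Both the intervention and control group will be given a 4 week supply of NRT lozenges with instructions of how to use". The mHealth Intervention section adds that "All participants (including the control group) will receive an NRT lozenge guide". The Nicotine Replacement Therapy subsections, one per arm with the same content, specify a mailed 4 mg lozenge. They name six side effects to be explained to participants, and add that "severe side effects (vomiting, syncope, tachycardia) related to use of the nicotine replacement are rare". For any effect possibly due to the lozenge, "we will instruct participants to stop using the lozenge and contact the study phone number to speak to a registered nurse"; severe effects go to the principal investigator, who is a registered nurse.

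On collection, Measures covers feasibility, acceptability, abstinence and quit attempts, baseline characteristics, and cessation resources. The nearest item, under Cessation Resources, asks both arms at the 30-day follow-up about use of any pharmacotherapy. Data Analysis & Statistical Considerations describes baseline characteristics, feasibility, acceptability and preliminary efficacy, and nothing on side effects or stopping.

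**The concern.** There are two linked gaps.

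- **The risk statement.** A list introduced as the only risks is closed. It cannot stand beside two subsections of the same protocol that name nine possible effects of a product the study supplies. The entry on risk from smokeless tobacco use does not naturally cover a study-supplied nicotine product.
- **Recording and reporting.** The team hears of a side effect only when a participant follows the instruction to call, and the protocol does not say that calls are logged. Nobody is asked whether they had an effect or stopped the lozenge because of one.

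The Background summary says that a successful pilot will be the basis for a larger trial. At the end of this one, the team could not say how well lozenge users tolerated a component given to everyone. Nor could it separate stopping for side effects from other stopping. That distinction matters here: the supply is for 4 weeks, while "Participants will be instructed to use the lozenges every day for 12 weeks", so some participants may stop simply because the lozenges ran out.

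**Working it through.** The plan gives no figure on this point to reproduce. The check is mainly a comparison of sections, followed by a short calculation of what the missing items could show.

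**Step 1. Named effects against the places where they should appear.**

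| Effects in the Nicotine Replacement Therapy subsections | In the risk list | In Measures | In the analysis plan |
|---|---|---|---|
| Six: headache, nausea, poor sleep, light-headedness, palpitations, mouth sores | 0 of 6 | 0 of 6 | 0 of 6 |
| Three severe and rare: syncope, tachycardia, vomiting | 0 of 3 | 0 of 3 | 0 of 3 |

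**Step 2. Could an existing item stand in?**

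- The pharmacotherapy question records use only. It asks about neither side effects nor stopping, and it is unclear whether it includes the study lozenge.
- The acceptability questions concern usefulness, change in use, thinking about quitting and recommending the program.
- The optional phone interview is there to expand on the engagement answers.
- The stop-and-call route produces reports, but only from those who call.

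**Step 3. What could be reported as written.** The proportion wanted is (lozenge users with the effect) / (lozenge users asked). Calls, if someone kept a record, would supply part of the numerator. No users are asked, so the denominator does not exist. Dividing calls by the 50 participants sent lozenges would give at best a crude lower bound.

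**Step 4. What survey items would add.**

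Inputs: 50 participants, 25 per arm, and the 80% retention target from Measures, Feasibility. The event rates of 10% and 1%, and the share of respondents who used the lozenge, are assumptions; the documents give neither.

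- All respondents used lozenges: n = 0.80 × 50 = 40.
- Half did: n = 0.50 × 40 = 20. One arm alone with full use gives the same number, 0.80 × 25 = 20.

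The chance of seeing an effect at least once is 1 − (1 − p)^n. Intervals are exact (Clopper-Pearson) 95%.

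| True rate p (assumed) | n = 40 | n = 20 |
|---|---|---|
| 10% | 1 − 0.90^40 = 98.5% | 1 − 0.90^20 = 87.8% |
| 1% | 1 − 0.99^40 = 33.1% | 1 − 0.99^20 = 18.2% |
| Interval if 10% is observed | 4/40: 2.8% to 23.7% | 2/20: 1.2% to 31.7% |

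If only half of one arm's respondents used the lozenge, n = 10 and the chance for a 10% effect is 1 − 0.90^10 = 65.1%.

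So survey items would show whether an effect at around 10% is occurring, with a wide interval. An effect at 1% would be missed with probability 67% (n = 40) to 82% (n = 20). For severe effects the call log matters more than the survey.

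**The case against.** The strongest case on the other side is about weight; it does not dispute the text.

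- **Participants are already protected.** They are told of all nine effects, receive a lozenge guide, have dosing limits and are instructed to stop and call for any possibly related effect. This stands. A reader might infer from the risk list that participants are not warned or that lozenge safety was ignored; the Nicotine Replacement Therapy subsections show otherwise.
- **No stated aim needs the missing proportion.** Aim 2 concerns feasibility, acceptability and preliminary efficacy of the mHealth intervention. The lozenge is background treatment, with dose and length modelled on similar studies. This also stands, and it limits the importance of the point. It does not remove the value of knowing tolerability before a larger trial.
- **The calling instruction is a standing one, and a crude denominator exists.** True, but the reporting is still passive, no log is specified, and calls over lozenges mailed is not the proportion among users who were asked.
- **The yield is small.** Agreed for rare effects and for by-arm figures. The rates used above are assumptions, and the protocol gives none for the six non-severe effects.
- **The consent form may list lozenge risks.** It may; consent pages are not in the public document. That would neither correct the risk section nor add a measure or summary.

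**Conclusion.** The concern holds in a limited form. The closed risk list conflicts with the protocol's own account of the lozenge: nine named effects, none in the list. No planned measure or summary covers side effects or stopping because of one. Followed as written, the pilot would have only phoned-in reports, with no specified log, and could not give either proportion among lozenge users. These conclusions rest on the text alone; the detection probabilities and intervals rest on assumed event and use rates.

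Two stronger readings are not supported. One is that the quit comparison is compromised: both arms get the same supply and the same instructions, so the recording gap does not invalidate it. The other is that the minimal-risk classification is wrong: nothing in the documents shows that naming the lozenge would change it. The point concerns an incomplete statement and what the pilot can report. It should be put right because the change is small and specific.

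**What to change.** 1. In the Risk/Benefit Assessment, add the lozenge effects already named in the Nicotine Replacement Therapy subsections, and keep the description of the severe ones as rare.
2. Log every side-effect call in REDCap with arm, date, event and action taken.
3. In the existing 30-day survey, next to the pharmacotherapy question, ask both arms whether the study lozenge was used, about when it was last used, which of the listed effects occurred, and whether it was stopped because of one.
4. In Data Analysis & Statistical Considerations, add one descriptive table among lozenge users, overall and by arm: each effect, and stopping because of an effect, with the numbers asked and answering. Count each participant once per effect, show whether the report came from the survey, a call or both, and do no test.

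The cost is a protocol amendment, a few items in a survey that is already planned, a simple log, one table and some staff time. The downsides are a slightly longer survey, some recall error, imprecise estimates at this size and little information on rare severe effects. Sample size, randomization and the efficacy analysis do not change.

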Feasibility. The feasibility outcomes will be: (a) the number of smokeless tobacco users recruited and randomized during the 4-month recruitment period; (b) engagement in the intervention measured by the portion of responses to messages that require a response; (c) the retention rates in the mHealth intervention compared to the control group at 30-days post intervention completion. We will determine

the feasibility by: (a) ability to recruit and enroll 50 participants in 4-months; (b) engagement with the intervention by having participants respond to at least 75% of messages or engage with 75% of the content using both self-report and objective methods. To calculate the proportion of messages read per participant, we will use a 5-point Likert scale to ask participants the following questions: "What did you typically do when you received a message from the mHealth intervention?" (1= ignored it completely, 5= read it immediately), "On a typical day, did you read messages you received?" (1= Not at all, 5= read the entire message), and On a typical day, did you engage with the intervention you received?"(1= Not at all, 5= read the entire message); and (c) ability to retain 80% of the sample at the 30-days follow-up. All participants will be given the option to participate in a phone interview with a member of the study team to expand on these answers approximately 1 month after their intervention has completed.

Acceptability and Consumer Satisfaction. To determine acceptability, we will ask the following questions using a 5-point Likert scale tailored to each arm of the study: 1) How useful was the intervention in helping you to quit smokeless tobacco (1 - Not at all useful, 5 = Extremely useful); 2) whether the intervention will change their smokeless tobacco use (1= Will not change at all, 5 = Will change a lot); 3) Did the intervention make you think about quitting (1= Not at all; 5 = All the time); and 4) Would you recommend the program to a friend (1 = Definitely would not recommend, 5 = Definitely would recommend). We will deem the pilot "acceptable" if each question has a mean level of 4 or higher.

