Descriptive statistics will be used to detail the baseline sample characteristic along with the feasibility, acceptability, and preliminary efficacy outcomes. The focus of the efficacy analyses will be on looking for a signal of intervention effect rather than statistical significance testing or effect size testing due to the small size and exploratory nature of this initial statistically underpowered pilot study. Non-directional statistical tests will be conducted, and the significance level will be set at 0.05 per test for this preliminary study. For the preliminary efficacy analyses, both intention-to-treat (ITT) and completers analyses will be conducted. The ITT analysis will include all participants randomized to an intervention group regardless of study or treatment completion, while the completer's analyses will include only those who finish the 30-day post-intervention completion assessment. For the ITT analysis, those who do not complete the 30-day assessment will be considered non-quitters.

Sample Characteristics. Intervention group differences in baseline sample characteristics will be tested using Wilcoxon Two-Sample Tests for continuous measures and Fisher's Exact tests for categorical measures due to the small sample size per group.

Feasibility. We will describe recruitment, enrollment, and 30-day follow-up attrition rates, as well as engagement with the intervention.

Acceptability. Participants' ratings of (a) the usefulness of the intervention received; (b) extent to which the intervention received changed their smokeless tobacco use, (c) whether the intervention made them think about quitting, and (d) whether or not they would recommend the program to a friend. We will compare intervention group differences in the acceptability using Wilcoxon Two-Sample Tests or Fisher's Exact Tests if when the acceptability ratings are dichotomized.

Preliminary Efficacy. The ST cessation (quit) rate per intervention group at 30-days post-intervention will be determined for the ITT and completers analyses using Fisher's Exact Tests.

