Power Analysis. Past ST cessation studies (both text and web-based) have yielded ITT quit rates in the 12%-20% range. We estimate that the mHealth intervention will yield similar quit rates. We expect that the quit rate for the control condition will likely be 5%-10%. Given the expected small to medium effect sizes (ORs: 1.44 to 2.47), a sample size of 50 (25/arm) will not provide 80% power to detect a statistically significant difference in quit rates with significance set at 0.05. Thus, the efficacy analyses will focus on looking for a signal of effect and that the intervention is trending in the right direction.

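### Low-cost improvement: for the non-primary efficacy outcome, report the between-arm difference in quit rates with an interval, and state that a favourable direction alone is not evidence of efficacy

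*Combined protocol and SAP*

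**What the plan says.** Design & Procedures makes feasibility and acceptability the primary outcomes; efficacy is assessed in addition. Under Measures (Preliminary Impact), the efficacy outcome is self-reported 7-day abstinence at 30 days post-intervention.

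Data Analysis & Statistical Considerations opens with a general statement: "Descriptive statistics will be used to detail the baseline sample characteristic along with the feasibility, acceptability, and preliminary efficacy outcomes". Its stated aim for the efficacy analyses is this: "looking for a signal of intervention effect rather than statistical significance testing or effect size testing due to the small size and exploratory nature". It also commits to non-directional tests at 0.05 per test and counts ITT participants without a 30-day assessment as non-quitters. Under Preliminary Efficacy, the quit rate per arm "will be determined for the ITT and completers analyses using Fisher's Exact Tests".

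Power Analysis notes that past studies "have yielded ITT quit rates in the 12%-20% range", expects similar rates for mHealth and 5-10% for control, and accepts that 25 per arm will not reach 80% power. It then concludes: "Thus, the efficacy analyses will focus on looking for a signal of effect and that the intervention is trending in the right direction".

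The primary outcomes are treated differently. Under Measures, one feasibility criterion is "ability to retain 80% of the sample at the 30-days follow-up", and the pilot is deemed acceptable "if each question has a mean level of 4 or higher".

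**The concern.** The plan says what it will look for in the efficacy data but not what summary will show it. Per-arm rates give a point difference without its uncertainty. Fisher's p-value gives no range of compatible effects, and it is the kind of result the plan says it will not focus on. What remains as the stated focus is direction.

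With 25 per arm and quit rates of 5-20%, each arm would have about 1 to 5 quitters (25 × 0.05 = 1.25; 25 × 0.20 = 5). A lead of one or two quitters could then be written up as the hoped-for trend. At stake is over-reading a small lead. No formal decision rests on it: the Background summary says a successful pilot will be the basis for a larger trial, but does not define success by efficacy.

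**Working it through.** **Inputs.** n = 25 per arm; mHealth quit rate 12-20%; control 5-10%; two-sided 0.05 (all from Data Analysis & Statistical Considerations). Usual Care Control reports 16-18% for the Enough Snuff program, so those values are included among the common rates. Assumptions of this check: a trend means any lead in quitters, and Newcombe's method is used for the illustrative intervals.

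**1. The plan's own statement.** Exact Fisher power is the sum of Bin(a; 25, p1) × Bin(b; 25, p0) over all pairs (a, b) with two-sided p ≤ 0.05. It is given in the table in step 4: 1% to 20%, far below 80%. The plan's statement on power is confirmed.

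**2. Chance leads with no true effect.** With a common rate p, P(mHealth leads) = Σ over a > b of Bin(a; 25, p) × Bin(b; 25, p), which by symmetry equals (1 − P(tie)) / 2. For example, at 10%: (1 − 0.191) / 2 = 0.405.

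| Common quit rate | mHealth leads | Tie | Of mHealth leads, 95% Newcombe interval includes zero |
|---|---|---|---|
| 5% | 36.4% | 27.3% | 99.3% |
| 10% | 40.5% | 19.1% | 96.4% |
| 16% | 42.3% | 15.5% | 94.2% |
| 18% | 42.6% | 14.7% | 93.9% |
| 20% | 42.9% | 14.1% | 93.8% |

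Control leads equally often. Fisher's test is also non-significant in 97.4-99.9% of these chance mHealth leads.

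**3. What an interval adds: 4/25 v 2/25.** The Wilson limits for one arm are (p + z²/2n ± z√(p(1−p)/n + z²/4n²)) / (1 + z²/n), with z = 1.96. They are 0.0640 to 0.3465 for 4/25 and 0.0222 to 0.2497 for 2/25. The difference is 0.16 − 0.08 = 0.08.
- Lower limit: 0.08 − √((0.16 − 0.0640)² + (0.2497 − 0.08)²) = 0.08 − 0.195 = −0.115.
- Upper limit: 0.08 + √((0.3465 − 0.16)² + (0.08 − 0.0222)²) = 0.08 + 0.195 = 0.275.

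The result would be +8 points, about −11 to +28, with Fisher p = 0.67.

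**4. At the plan's expected rates (25 per arm).**

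| mHealth v control | Fisher power | mHealth leads | Of leads, Newcombe includes zero | Of leads, Fisher p > 0.05 | Mean Newcombe width |
|---|---|---|---|---|---|
| 12% v 10% | 1.3% | 50% | 94.2% | 97.9% | 37.8 points |
| 12% v 5% | 2.9% | 74% | 89.8% | 96.1% | 35.7 points |
| 20% v 10% | 8.6% | 79% | 79.9% | 89.2% | 40.4 points |
| 20% v 5% | 19.8% | 93% | 64.4% | 78.7% | 38.4 points |

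For completers, if 20 per arm finish (the 80% retention target split evenly, an assumption), the mean width is 41-45 points.

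**5. Does the interval agree with the planned test?** Not always. Step 4 shows that Newcombe's interval includes zero less often than Fisher's test is non-significant. At 8/25 v 2/25 the Wilson lower limit for 8/25 is 0.1721, so the Newcombe lower limit is 0.24 − √((0.32 − 0.1721)² + (0.2497 − 0.08)²) = 0.24 − 0.225 = +0.015, while Fisher p = 0.074. The interval also excludes zero at 5 v 0 (Fisher p = 0.050, just above the cut) and 6 v 1 (p = 0.098). Fisher needs 6 v 0, 7 v 1 or 9 v 2.

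**The case against.** The best case for the plan is that it already guards against over-reading. It commits to two-sided tests, names Fisher's test for both ITT and completers, and calls the study exploratory and underpowered. A 4 v 2 result would appear as 16% v 8% with p = 0.67, which is itself a warning. Efficacy is not primary, the difference can be worked out from the planned rates, and the numeric criteria used for contrast belong to the primary outcomes.

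Much of this stands, and it rules out several stronger readings:
- A reader might infer that nothing in the plan restrains how a lead is described. That goes too far: the Fisher test and the disclosed low power are real restraints.
- A reader might infer that the plan adopts any lead as its success rule. It states no such rule. The 36-43% figure describes an assumed reading.
- A reader might treat low power as the fault, or think a go/no-go decision hangs on this result. The first is disclosed and the second appears nowhere.
- A reader might think any small-sample interval is a stricter guard than the planned test. Newcombe's is more permissive at some counts.

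What survives is narrow. Power Analysis turns to direction precisely because the test is not expected to reach significance, so a non-significant p-value only partly checks a claim based on direction. Setting effect size testing aside is no obstacle either, because a difference with an interval is estimation.

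**Conclusion.** The point holds as a low-priority improvement to the presentation and reading of a non-primary outcome. It is not a design fault. The gap in the wording is plain from the text: neither a signal nor a trend is defined, and no between-arm difference or interval is named.

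The size depends on reading a trend as any lead. On that assumption, with 25 per arm and no true effect, mHealth leads 36-43% of the time at common rates of 5-20%. Even at the plan's expected rates, 64-94% of mHealth leads would have a 95% Newcombe interval that includes zero. The benefit is limited to showing that uncertainty beside the direction, and it requires an interval that does not undercut the planned exact test.

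**What to change.** Add wording of this kind to Preliminary Efficacy in the SAP:

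> The efficacy summary is the ITT difference in 7-day quit rate at 30 days post-intervention (mHealth minus control) with a 95% small-sample interval. The same summary is given for completers. The Fisher p-value is reported beside each. A favourable direction alone will not be described as evidence of efficacy.

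Then settle the interval method in one of two ways:
- Use an exact interval consistent with the exact test. Exact intervals for a difference and Fisher's test are built differently, so check agreement over the 26 × 26 = 676 possible ITT tables before data are seen.
- Or use Newcombe's interval, state in advance that it can exclude zero when Fisher p > 0.05 (for example 5 v 0, 6 v 1 and 8 v 2 of 25), and say that such results will not be called evidence of efficacy.

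No numeric threshold for a signal is needed for an exploratory outcome.

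The cost is a few sentences and a few lines of code, with no new data and no design change. The interval will be wide (about 36-40 points on average by Newcombe at the stated rate pairs; an exact interval may be wider). The efficacy statement will be less favourable than one based on direction, and the interval will not size the next trial.
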